After gathering this feedback and incorporating it into the intervention design and content, we will present the updated intervention to the firefighters and EMTs in a second workshop to obtain their feedback on the design and content. We will use feedback to refine the intervention. We will then conduct usability testing during the third workshop. Usability testing will comprise: 1) observing smokeless tobacco users interacting with the intervention, guided by “concurrent think aloud” protocols, and taking field notes; and 2) gathering feedback through semi-structured interviews immediately following the use of the intervention. Overall usability of the intervention will be measured by adapting the System Usability Scale (SUS), a validated tool provided by the US Department of Health and Human Services, which consists of 10 items rated from “strongly disagree” to “strongly agree” (e.g., “I thought the intervention was easy to use” and “I felt very confident using the intervention”).

Aim 2: To assess the feasibility, acceptability and preliminary efficacy of the mHealth intervention compared to a usual care control intervention in decreasing smokeless tobacco use.

Objective: To determine if the mHealth intervention is feasible and acceptable for smokeless tobacco cessation for first responders such as firefighters and EMTs. We will also evaluate preliminary efficacy of the intervention in decreasing smokeless tobacco use.

Methods and Strategy:

Recruitment and Data Collection: We will recruit 50 smokeless tobacco users from collaborating Central North Carolina Fire Stations, and from social media ads that will run nationally in the United States. Inclusion criteria: 1) 18 years of age and older; 2) Employed as a professional firefighter or EMT / paramedic; 3) Have used smokeless tobacco for the last year and current (past 30 days) smokeless tobacco daily use; 4) Have access to a smart cell phone.

Randomization: Eligible participants will be randomized to either the mHealth Intervention (N=25) or control (N=25) group. Computerized randomization will be used to deliver a permuted block randomization with block sizes of four that will be used to randomly assign participants to one of the two intervention groups. The randomization scheme generated by the study statistician will be administered using the REDCap system.

Intervention:

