Motivational Text-Messages: To deliver the most equivalent intervention to the original Enough Snuff Program, we will send participants motivational text messages that map to the content of the phone counseling sessions. One week after the cessation booklet is sent we will text participants twice a week for the next 10 weeks. These are separate texts than what the intervention group will receive and coincide with the Enuf Snuff booklet. We will model the messages after the phone content and messages will focus on: motivation to quit, setting a quit date, picking a quit plan, motivation to follow-through with plan and dealing with tough situations when quitting. Messages will refer to the Enough Snuff booklet ask for a response from participants. We chose to send text messages to participants instead of phone calls as texting is consistent with our mode of contact with participants, less expensive, expands our reach, and is highly acceptable according to our pilot work.

Nicotine Replacement Therapy: We will provide participants via mail nicotine replacement the nicotine lozenge at no cost. We will provide a 4 week supply of 4mg Lozenge (mirroring the dose and the length to similar studies with smokeless tobacco users) with instructions on how to use. Participants will be instructed via text to start their NRT on their quit date. Participants will be instructed to use the lozenges every day for 12 weeks. For the first 6 weeks, use 1 lozenge every 1-2 hours. For the next three weeks, use 1 lozenge every 2-4 hours. For the last three weeks, use 1 lozenge every 4-8 hours. They should not use more than 5 lozenges in 6 hours, or more than 20 lozenges total per day. For any side effects potentially related to use of the nicotine replacement, we will instruct participants to stop using the lozenge and contact the study phone number to speak to a registered nurse (PI is a registered nurse). We will explain side effects that include nausea, light-headedness, headache, poor sleep, mouth sores and heart palpitations. We will explain that severe side effects (vomiting, syncope, tachycardia) related to use of the nicotine replacement are rare; however, we will make participants aware of these and will instruct them to contact the PI (a registered nurse) if they occur.

Measures

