Randomization: Eligible participants will be randomized to either the mHealth Intervention (N=25) or control (N=25) group. Computerized randomization will be used to deliver a permuted block randomization with block sizes of four that will be used to randomly assign participants to one of the two intervention groups. The randomization scheme generated by the study statistician will be administered using the REDCap system. We will also use a graded compensation for surveys with \$15 for baseline and \$20 for 30-days post end of program.

Risk/Benefit Assessment

This is a minimal risk study. The only risks are the potential for emotional distress in answering questions about smokeless tobacco use and the risk associated with smokeless tobacco use, and the potential loss of confidentiality. Every precaution will be taken to minimize these risks, including the ability to contact the PI for questions or concerns, and using encrypted devices to record PHI.

All participants may decline to be part of the study and may leave the study at any time without loss of benefit to which they are entitled.

The focus groups will be conducted in the firefighters' home station or individually via Zoom. Participants in focus groups will be familiar with each other and will be free to respond or not respond. Firefighters and EMTs will have the PI's email address and can message if they prefer to respond privately.

Intervention participants may choose the time and the place to take their surveys and respond or not respond to Mosio secure text messages. This will ensure their comfort with the privacy available to them. All study platforms will be secure and approved by Duke OIT, helping to ensure participant response confidentiality.

The potential benefits outweigh risks. Those who participate in the intervention have a high probability of benefitting if they decrease or cease using smokeless tobacco.

Data Analysis & Statistical Considerations

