Descriptive statistics will be used to detail the baseline sample characteristic along with the feasibility, acceptability, and preliminary efficacy outcomes. The focus of the efficacy analyses will be on looking for a signal of intervention effect rather than statistical significance testing or effect size testing due to the small size and exploratory nature of this initial statistically underpowered pilot study. Non-directional statistical tests will be conducted, and the significance level will be set at 0.05 per test for this preliminary study. For the preliminary efficacy analyses, both intention-to-treat (ITT) and completers analyses will be conducted. The ITT analysis will include all participants randomized to an intervention group regardless of study or treatment completion, while the completer's analyses will include only those who finish the 30-day post-intervention completion assessment. For the ITT analysis, those who do not complete the 30-day assessment will be considered non-quitters.

Sample Characteristics. Intervention group differences in baseline sample characteristics will be tested using Wilcoxon Two-Sample Tests for continuous measures and Fisher's Exact tests for categorical measures due to the small sample size per group.

Feasibility. We will describe recruitment, enrollment, and 30-day follow-up attrition rates, as well as engagement with the intervention.

Acceptability. Participants' ratings of (a) the usefulness of the intervention received; (b) extent to which the intervention received changed their smokeless tobacco use, (c) whether the intervention made them think about quitting, and (d) whether or not they would recommend the program to a friend. We will compare intervention group differences in the acceptability using Wilcoxon Two-Sample Tests or Fisher's Exact Tests if when the acceptability ratings are dichotomized.

Preliminary Efficacy. The ST cessation (quit) rate per intervention group at 30-days post-intervention will be determined for the ITT and completers analyses using Fisher's Exact Tests.

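### The protocol fixes and prints a single block size of four, so anyone who tracks past allocations could work out about a third of the assignments; undisclosed, randomly varied block sizes would remove most of that certainty at little cost

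*Combined protocol and SAP*

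**What the plan says.** The Randomization paragraph appears twice in the combined protocol and SAP in the same terms: under Aim 2, Methods and Strategy, and again after Recruitment in Selection of Subjects. It sets the target, "Eligible participants will be randomized to either the mHealth Intervention (N=25) or control (N=25) group", and the method, "permuted block randomization with block sizes of four that will be used to randomly assign participants to one of the two intervention groups". On control of the sequence it says "The randomization scheme generated by the study statistician will be administered using the REDCap system".

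Neither place mentions strata, varying block sizes, masking, concealment of the sequence from enrolling staff, or any limit on who may see earlier assignments.

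The Intervention section shows that the arms can be told apart. The mHealth arm gets support texts two or three times a day with interactive keywords. The control arm gets a booklet, by link and in hard copy, and texts twice a week. Of the control texts the protocol says "These are separate texts than what the intervention group will receive and coincide with the Enuf Snuff booklet".

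**The concern.** With a short block of known length, the assignments already made in a block limit those still to come. Once one arm's two places are used, the rest of the block is fixed. Keeping the list inside REDCap does not change this, because the inference needs only the block size, which the protocol prints, and the past assignments, which are visible to whoever delivers the arm-specific material.

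If a person with that knowledge could also influence who is enrolled next, or when, participants could be steered towards one arm, even without intent. There is room for this to matter. The eligibility criteria cover age, occupation, daily use and phone access, and do not restrict readiness to quit, so motivation may vary widely among eligible people. The Power Analysis section says efficacy will be read as a signal and a direction of effect, which a modest imbalance in motivation could influence. Acceptability ratings and retention are also compared between arms and would be open to the same imbalance.

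**Working it through.** **Inputs from the documents.** Block size 4, allocation 1:1 and total 50, all from the Aim 2 recruitment and randomization text. The sequence is treated as a single list because no strata are described.

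**Assumption.** The observer knows the block size and every earlier allocation. The documents neither state nor exclude this.

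**Fixed blocks of four, by enumeration.** A block with two places per arm has 6 equally likely orders. An allocation is determinable when one arm's places in the block are used up. The best guess is the arm with more places left, or a coin toss when they are equal.

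| Order | Determinable places | Expected correct guesses |
|---|---|---|
| AABB | 2 | 2.5 |
| ABAB | 1 | 3 |
| ABBA | 1 | 3 |
| BAAB | 1 | 3 |
| BABA | 1 | 3 |
| BBAA | 2 | 2.5 |

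- Determinable: 8 of 24 places = 33.3%, or 4/3 per block. The fourth place is always determined, and the third is determined one time in three.
- Correct guesses: 17 of 24 = 70.8%, or 17/6 per block.

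**At 50 participants.** 50 = 12 full blocks + 2.

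- Determinable: 12 × 4/3 + 0 = 16 expected, and 16/50 = 32%. The range is 12 (one per block) to 24 (two per block).
- Correct guesses: 12 × 17/6 = 34 from the full blocks. The last two places add 1/2 + 2/3 = 7/6. The total is 211/6 = 35.2, and 35.2/50 = 70.3%.
- Simulation agrees: 32.0% and 70.3%.

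**Randomly varied blocks of 4, 6 and 8.** These were simulated for 50 allocations with the three sizes equally likely. The observer knows the possible sizes but not their order, and updates after each allocation. About 2.4% are determinable and about 67.7% are guessed correctly.

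**Single permuted list of 50, with m = 25 per arm.**

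- Determinable share: 1/(m + 1) = 1/26 = 3.8%.
- Correct guesses: [m + (2^(2m)/C(2m, m) − 1)/2]/(2m). For m = 25, 2^50/C(50, 25) = 8.91, so (25 + 7.91/2)/50 = 57.9%.

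**Balance if recruitment stops early.**

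| Scheme | Determinable | Guessed | Imbalance on early stop |
|---|---|---|---|
| Fixed blocks of 4 | 32% | 70.3% | at most 2 |
| Random 4, 6, 8 | about 2.4% | about 68% | at most 4 |
| Single list of 50 | 3.8% | 57.9% | at 40 randomised, one arm has 17 to 23 (95% range); 29% chance of a difference of 4 or more |

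The last row uses the hypergeometric distribution: 40 drawn from a list holding 25 of each arm.

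**The case against.** The strongest reply is that the plan describes no route by which the knowledge could be used. The statistician generates the sequence and REDCap administers it, so generation is separate from assignment. The screening and consent steps that the protocol spells out belong to the Aim 1 workshops. For Aim 2, recruitment includes national social media advertising, and no passage says that staff can hold back or reorder candidates. Readiness to quit and dependence are measured at baseline and compared between arms, so a large imbalance would at least be reported, although 25 per arm limits what such a comparison can detect. The primary outcomes are feasibility and acceptability, and the efficacy analysis is declared underpowered.

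Most of this stands, and it limits how far the point goes. Four stronger readings are tempting, and the documents do not support them.

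- **One unblinded team enrols and delivers.** A reader might infer this. Visible arms are a fair inference from the arm content, but the protocol does not say who enrols Aim 2 participants, whether they see past allocations, or whether they control timing.
- **The efficacy signal would be biased by about 4 points.** Suppose every enrolment were steered by best guess, with prospects of 20% and 10% quit chance. The false difference would be (2 × 0.703 − 1) × 10 = 4.1 points. That is an assumed worst case. It compares with a standard error of about 8.5 points, √(2 × 0.1 × 0.9/25), and with expected differences of 2 points (12% against 10%) to 15 points (20% against 5%). Varied blocks would bring it only to (2 × 0.677 − 1) × 10 = 3.5 points.
- **Small blocks serve no purpose here.** They do. Recruiting 50 in four months is itself a feasibility outcome, and blocks of four keep the arms within two participants wherever recruitment stops.
- **Failing to guarantee 25/25 is a defect.** Blocks of four give 25/25 with probability 2/3 and otherwise 26/24. The effect on precision is negligible: the standard error rises by about 0.08%.

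The reply does not remove the core of the point. The block size is fixed and disclosed, past assignments can be seen by whoever delivers the arms, and the plan states no barrier between that knowledge and enrolment.

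**Conclusion.** The concern holds as a minor, avoidable weakness in the allocation method. For an observer who knows the block size and all earlier assignments, 16 of 50 allocations (32%; 33.3% within a full block) are determinable and about 70% are guessable. These figures rest on that observer existing and on a single unstratified sequence. Harm would also require influence over enrolment. The documents are silent on the observer's knowledge and on that influence, so they show an open risk and not that selection bias would occur. It is still more than a gap in reporting, because the stated method can be replaced by one that leaves very few allocations certain.

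**What to change.** In both Randomization paragraphs, replace the fixed size of four with randomly varied block sizes (for example 4, 6 and 8). Let only the statistician hold the sizes and their order, and do not name them in documents available to enrolling staff. State also who enrols Aim 2 participants and whether they can see earlier allocations.

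The cost is a short text change in two places, a new REDCap allocation table, and a possible imbalance of up to four participants instead of two if recruitment stops mid-block. The gain is mainly the loss of certainty (32% to about 2.4%); guessing improves little (70% to about 68%).

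A single permuted list of 50 would lower guessing further, to about 58%, but it gives up balance if recruitment falls short. It is an option for the sponsor to weigh and not the required change.

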Development of a M-Health Smokeless Tobacco Cessation Intervention for Firefighters

Document Date: 2/22/2024

NCT05111041

Purpose of the Study

The specific aims are:

Aim 1: In collaboration with the Professional Firefighters and Paramedics of North Carolina and our Advisory board of firefighters, develop a mHealth smokeless tobacco cessation intervention tailored to the specific needs of first responders such as firefighters and EMTs / paramedics. Using a co-facilitated user centered design approach and guided by the Spiral Technology Action Research Model (STAR) Model, we will work with firefighters & EMTS / paramedics to 1) identify and develop intervention content, messaging, and m-health modalities for delivery (e.g., text-messaging, text-chat); 2) refine the intervention; and 3) conduct usability testing. The outcome of Aim 1 will be a fully developed mHealth smokeless tobacco cessation intervention tailored to the unique needs of first responders (e.g., firefighters and EMTs) that is ready for pilot testing.

Aim 2: To assess the feasibility, acceptability, and preliminary efficacy of the tailored smokeless tobacco cessation intervention compared to a usual care control intervention in decreasing smokeless tobacco use. This aim will specifically address recruitment and retention to determine feasibility, acceptability as measured by the usefulness of the intervention received, and preliminary efficacy of the intervention in improving smokeless tobacco cessation at 30-days post intervention completion as measured by self-reported abstinence from smokeless tobacco use. This evaluation will be done with 50 firefighters & EMTs / paramedics who use smokeless tobacco who will be randomized to the tailored mHealth intervention (n=25) or the usual care control (n=25) of a self-help booklet. Both the intervention and control group will be given a 4 week supply of NRT lozenges with instructions of how to use.

Background & Significance

Firefighters are at high risk for cancer

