mHealth Intervention: Although the specific content, messaging and delivery strategy will be developed with firefighters and EMTs, the proposed mHealth intervention will incorporate evidenced-based strategies for cessation and theoretical constructs from the Social Cognitive Theory and the Health Belief Model that have been shown to support cessation. The intervention will contain key steps to quitting including: 1) supporting readiness and motivation to quit; 2) setting a quit date and constructing a quit plan; 3) dealing with withdrawal symptoms and triggers to use; and 4) maintaining quit status and avoiding relapse.

Participants will identify on the baseline survey whether they would prefer to quit by reduction or by abrupt cessation. All participants will receive support messages and NRT. All participants (including the control group) will receive an NRT lozenge guide (to provide instructions to all participants to create a consistent use for all). This will be included when the NRT lozenges are sent out to each study participant.

Abrupt Cessation: Participants are asked to set a quit date within two-four weeks. This quit date is emailed to participants. Participants will receive 8 weeks of messages. Pre-quit messages will focus on health benefits of quitting, building confidence, and making a quit plan. Post-quit messages will focus on dealing with cravings and urges and relapse prevention.

Reduction Cessation: Participants will receive a text at the beginning of each week alerting them to their number of dips for each day that week. They will receive a message reminder in the morning: "Do your best to only dip X times today, limit dip in your mouth to 30 minutes." At the end of each day participants will be asked to report how many times they dipped that day.

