Text-based Cessation Support Intervention: Participants will receive text-based support messages 2-3 times per day over ten weeks. The messages are based on constructs of Social Cognitive Theory the Health Belief Model and the Theory of Self-regulation. Messages were developed from our pilot work with firefighters and address salient features that are associated with smokeless tobacco use in this population such as stress. The text-based system with have interactive capabilities, participants can text the word CRAVE if they are having a craving and will receive a message to help them deal with the craving. Participants can also text the word SLIP if they have a slip after their quit date and will receive a message to get them back on track. Participants can text MOOD if they need a positive message to boost their mood. Finally, participants can text the word CALL, a feature that can be used to address the stress that is commonly felt post-call. Messages will focus around providing mindfulness and deep breathing activities to deescalate after participating in a call.

Nicotine Replacement Therapy: We will provide participants via mail nicotine replacement the nicotine lozenge at no cost. We will provide a 4 week supply of 4mg Lozenge (mirroring the dose and the length to similar studies with smokeless tobacco users) with instructions on how to use. Participants will be instructed via text to start their NRT on their quit date. Participants will be instructed to use the lozenges every day for 12 weeks. For the first 6 weeks, use 1 lozenge every 1-2 hours. For the next three weeks, use 1 lozenge every 2-4 hours. For the last three weeks, use 1 lozenge every 4-8 hours. They should not use more than 5 lozenges in 6 hours, or more than 20 lozenges total per day. For any side effects potentially related to use of the nicotine replacement, we will instruct participants to stop using the lozenge and contact the study phone number to speak to a registered nurse (PI is a registered nurse). We will explain side effects that include nausea, light-headedness, headache, poor sleep, mouth sores and heart palpitations. We will explain that severe side effects (vomiting, syncope, tachycardia) related to use of the nicotine replacement are rare; however, we will make participants aware of these and will instruct them to contact the PI (a registered nurse) if they occur.

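### Both arms are mailed a 4-week lozenge supply but told to use lozenges daily for 12 weeks, and the optional saliva nicotine test has no rule for reading a positive result in a lozenge user

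*Combined protocol and SAP*

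**What the plan says.** **Supply.** Purpose of the Study, Aim 2: "Both the intervention and control group will be given a 4 week supply of NRT lozenges". The Nicotine Replacement Therapy paragraphs, which read the same under the mHealth intervention and under Usual Care Control, describe the supply as "We will provide a 4 week supply of 4mg Lozenge (mirroring the dose and the length to similar studies with smokeless tobacco users").

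**Instruction.** The same paragraphs say "Participants will be instructed via text to start their NRT on their quit date" and "Participants will be instructed to use the lozenges every day for 12 weeks". The schedule opens with "For the first 6 weeks, use 1 lozenge every 1-2 hours", then gives three weeks at 2 to 4 hour intervals and three weeks at 4 to 8 hours. It is limited by "They should not use more than 5 lozenges in 6 hours, or more than 20 lozenges total per day". The mHealth Intervention section adds that "All participants (including the control group) will receive an NRT lozenge guide", intended to make use consistent. The guide is not among the documents.

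**Timing.** Under Abrupt Cessation, "Participants are asked to set a quit date within two-four weeks", with 8 weeks of messages. The Text-based Cessation Support section gives ten weeks. Control texts start one week after the booklet is sent and run for 10 weeks. Outcomes are taken 30 days after the intervention.

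**Verification.** Measures, Preliminary Impact: those who report 7 days without tobacco may opt in to a saliva sample, which receives a nicotine test. No cut-off is given, and no rule for lozenge users. Cessation Resources asks both arms about any pharmacotherapy use at follow-up. The Data Analysis section gives the saliva result no role.

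**The concern.** The supply sentence presents four weeks as a course length taken from similar studies, and the lines that follow prescribe three times that. A participant who uses a 28-day supply over 28 days runs out in week 4, before any step-down. The documents mention no refill, second mailing or purchase. A lozenge guide meant to standardise use cannot do so if it carries two durations, and a larger trial built on this pilot would not know what lozenge exposure it was reproducing.

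The two durations also decide whether lozenge nicotine may be present at the assessment. A nicotine test cannot by itself tell a lozenge from tobacco. The participant who follows the 12-week instruction most faithfully could therefore be the one whose abstinence claim appears to be contradicted. The existing pharmacotherapy question partly identifies such people, but as described it has no 7-day window, no date of last use and no link to the saliva result.

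**Working it through.** **1. Duration.** Steps of 6 + 3 + 3 weeks = 12 weeks = 84 days. The plan's 12-week figure is reproduced, so it is not a slip. Supply: 4 × 7 = 28 days.

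**2. Lozenges needed.** Assumption: 16 waking hours a day. At one per hour, the limit of 5 in any 6 hours allows 5 + 5 + 4 = 14 in 16 hourly slots.
- Low rate (longest intervals): 42 × 8 + 21 × 4 + 21 × 2 = 462.
- High rate (shortest intervals, capped): 42 × 14 + 21 × 8 + 21 × 4 = 840.

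The pack count is not given, so three packs are assumed:

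| Assumed pack (28 days) | Against 462 | Against 840 |
|---|---|---|
| 8/day = 224 | short 238 | short 616 |
| 14/day = 392 | short 70 | short 448 |
| 20/day (daily cap) = 560 | 98 spare | short 280 |

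With pack and use at the same rate, the shortfall is 238/462 = 52% or 448/840 = 53%.

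**3. Follow-up against the 84 days.** Lozenges start on the quit date, so the instructed course ends on quit day + 84. For mHealth abrupt quitters (quit day 14 to 28) that is day 98 to 112.

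If messages run from enrolment and their end defines completion:
- 8 weeks: 56 + 30 = day 86, which is 12 to 26 days before the course ends. It is inside for every quit date in the window.
- 10 weeks: 70 + 30 = day 100. It is inside if the quit date is later than 100 − 84 = day 16. With quit dates assumed uniform over days 14 to 28, that is (28 − 16)/14 = 86%.
- Control: 7 + 70 + 30 = day 107 after booklet mailing, inside if the quit date is later than 107 − 84 = day 23. No control quit window is stated, so no share can be given. The same is true of the reduction path.

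Other readings of completion:
- The 8 weeks run from the quit date: follow-up at quit + 56 + 30 = quit + 86, which is 2 days after the course ends.
- The lozenge course counts as part of the intervention: follow-up at quit + 84 + 30 = quit + 114, which is 30 days after.

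If instead the supply is used up in 28 days, lozenges end on day 42 to 56. That is 86 − 56 = 30 to 100 − 42 = 58 days before the mHealth follow-up.

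**4. Claims exposed to the test.** From the quit rates in Power Analysis: 25 × 0.12 + 25 × 0.05 = 4.25, up to 25 × 0.20 + 25 × 0.10 = 7.5. That is about 4 to 8 abstinence claims in the whole trial. The number opting in to saliva is unknown.

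**The case against.** **The endpoint is self-report.** This stands. Saliva is opt-in, nobody is reclassified on it, and the Fisher tests do not use it. A reader might infer that the lozenge instruction distorts the quit rate or the comparison between arms. The documents do not support that: supply and instruction are the same in both arms, and the outcome asks about smokeless tobacco, not nicotine.

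**The timing depends on an unstated anchor.** This also stands. A reader might take from the 100% and 86% above that most quitters would test positive. Those are shares whose instruction is still open under one reading of completion, and the 86% also needs an assumed spread of quit dates. They are not shares using lozenges, and under other readings the course is over by follow-up. What survives is that follow-up can fall inside the course. The enrolment reading is not far-fetched, since the 8 weeks of messages include pre-quit ones.

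**The shortfall is not established.** This stands in part. A reader might infer that every participant runs out. A pack filled at the daily cap would cover the low-rate course, though 20 a day exceeds the 14 that the 6-hour limit allows in a 16-hour day. The count is needed to settle it.

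**Unseen instruments may fill the gap.** They may. The guide and the follow-up survey are not in the documents, so the amount used and any lozenges obtained elsewhere are not stated to be recorded. It does not follow that they are not recorded.

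**Conclusion.** The mismatch holds on the text alone and in both arms: a 28-day supply, an 84-day instruction, no step-down before week 7, and no stated source for the remainder. In lozenges the size can only be bounded. It is roughly half the course when pack and use run at the same rate, and 0 to 616 lozenges across the packs assumed here, on a 16-hour day.

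The verification gap is real but small and conditional. It needs a participant who is abstinent, still using lozenges at the assessment, and willing to give saliva, with a follow-up that falls within or close to the 84 days. The documents do not allow the frequency of that combination to be estimated. At most it touches the optional verification of about 4 to 8 claims.

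The documents also do not show which duration the sponsor intended, nor that participants are expected to buy the rest. The supply sentence is compatible with an intended 4-week course.

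**What to change.** **1. Settle duration and supply.** The sponsor states which duration is intended and how many lozenges are mailed, and both Nicotine Replacement Therapy paragraphs and the lozenge guide are made to agree.
- If 12 weeks: say how lozenges beyond the supplied amount are obtained.
- If 4 weeks: replace the schedule with one that steps down within 4 weeks. Cutting the present one short would leave no step-down. This is a dosing change, not a wording edit.

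**2. Extend the Cessation Resources item**, in both arms at the 30-day follow-up, and repeat it when saliva is collected:
- any lozenge or other non-tobacco nicotine product in the past 7 days;
- date of the last lozenge;
- whether any lozenges were obtained beyond those mailed.

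**3. Add a reading rule under Preliminary Impact:**
- negative result: supports abstinence, whatever the lozenge use;
- positive result with recent nicotine product use: indeterminate, not a false claim;
- positive result without such use: does not confirm abstinence.

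The self-reported outcome and its analysis stay as they are. The rule works whichever way completion is defined.

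**Cost.** A few added survey items, repeated at sampling, and edits to two paragraphs and the guide. Some positive results will be reported as indeterminate. Negative results in lozenge users are kept, so no informative sample is discarded.
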